7.4 Baseline Visit: Treatment Visit (Day 0)

The Baseline Visit (Day 0) will occur 7 to 14 days after the Screening Visit to allow for rescue medication washout. The injection will occur at this Baseline visit along with the following activities:

Before Treatment Injection

- Concomitant Medications
- Current non-drug therapies
- Confirm Medication Washout
 - If subject did not complete medications washout, reschedule the visit to allow washout to be completed.
- Patient Global Assessment (PGA)
- DASH index shoulder
- Index & Contralateral Shoulder Joint Pain (NRS Scale)
 - o Confirm Baseline Inclusion & Exclusion Criteria for NRS pain
- Physical Exam of Index and Contralateral Shoulder Joints

Treatment Procedure

The Treating Physician will always perform the Study Injection to the index joint as standard of care dictates.

Intra-articular injection of the shoulder joint should be conducted under fluoroscopic or ultrasound guidance. Guidelines for the injection procedural steps are provided below. Modifications to this technique should be recorded in the CRF

- Patient may be sitting or supine as required.
- Prep the skin at injection site with 1% betadine solution or equivalent.
- Peri- articular injection site anesthesia of lidocaine or topical refrigerant anesthetic (e.g. ethyl

chloride) may be utilized.

- Use fluoroscopic or ultrasound guidance to insert 18-22 1 cm lateral and 1 cm cephalad to the coracoid process. Insert the needle directed 20° medially and 60° caudally to enter the joint.
- Insert needle until resistance against the articular surface and then withdraw the needle 1-2 mm.
- If using fluoroscopic guidance, a small amount of fluoroscopic contrast agent (0.5 to 1.0 ml) should be injected through the needle to verify intra-articular placement.
- If using ultrasound guidance, a small volume of air (up to 0.5 ml) may be injected to verify IA positioning.
- If pooling of the contrast agent or air around the needle tip is observed, the needle should be repositioned.
- When contrast agent or air is successfully injected into the joint, intra-articular placement is confirmed.
- Following confirmation of intra-articular needle placement, the joint may be aspirated to remove synovial fluid.
 - o Confirm the Baseline Exclusion for synovial aspirate.
- 4 ml of MONOVISC is injected into the joint.
- Intra-articular anesthetic should NOT be administered as part of the injection procedure.
- Following the injection, the patient should be advised to maintain a low level of physical activity for the next 48 hours. Cold therapy and/or acetaminophen/ paracetamol may be prescribed to address short term injection site pain.

Post-Treatment Assessments and Instructions

Prior to leaving the clinic, the subject should be evaluated for local and non-local AEs. All post-treatment signs and symptoms that are unexpected should be recorded as AEs. The expected appearance of the index joint should be discussed with the subject with a request that all unexpected symptoms be reported to a member of the study team.

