4.2 Risks

Any intra-articular injection poses potential risks. However, subjects should incur no additional risks compared to injections of other frequently injected products, such as corticosteroids or diagnostic contrast agents.

Adverse events associated with single intra-articular knee injections of MONOVISC can be found in the MONOVISC Instructions for Use. These events are expected to be similar for shoulder injections. In the clinical trial for MONOVISC in knee OA, adverse events that were related to the injection treatment were:

- injection site pain/swelling
- joint stiffness / swelling / effusion
- arthralgia,
- pain in extremity
- synovitis

- contusion
- subcutaneous nodule
- Baker's cyst

Adverse events not related to the index joint for MONOVISC were:

- arthralgia
- headache
- pain in extremity
- upper respiratory tract infection
- back pain

Other risks associated with intra-articular shoulder injections, regardless of treatment, include:

- · temporary injection site pain, swelling or tenderness
- temporary stiffness of the shoulder
- malfunction of the syringe and/or needle

In rare instances, side effects could include:

- an allergic reaction to the fluoroscopic imaging contrast agent. Symptoms could include redness or inflammation at the injection site or inside the shoulder joint, hives or itching.
- an allergic reaction to the local anesthetic (lidocaine). Symptoms could include redness or inflammation at the injection site or inside the shoulder joint, hives or itching.
- injection site infection
- neurovascular, cartilage, or bone damage resulting from the injection itself

Finally, there is a low risk associated with radiation from the X-ray evaluation required for inclusion in the study. There is also a low risk from the radiation during fluoroscopy-guided injections

5. Contraindications / Warnings and Precautions

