6.5 Trial Design

This is a prospective, post market clinical follow-up (PMCF) multi-center, open-label study to evaluate the residual risk of injections of MONOVISC for relief of pain in patients with a diagnosis of an osteoarthritic shoulder joint.

The subjects in this study will be patients with a diagnosis of osteoarthritic (OA) joint who the investigator determines are appropriate candidates for treatment with a viscoelastic injection of MONOVISC.

Up to 25 subjects will be enrolled at up to 20 investigational sites in the EU. Subject participation will last approximately 6 Months, with visits scheduled at Screening, Baseline, 1 month, 3 month and 6 months.

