7.3.9.6 Subject Diary

Subjects will receive diary for to record rescue medications and concomitant medications.

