8. ADVERSE EVENTS

8.1 Reporting

8.1.1 Adverse Events

All AEs that occur during or after injection will be recorded. Worsening of a condition that existed prior to the study injection should be recorded as an AE. At each assessment during the trial, AEs that have occurred since the previous assessment must be recorded. All subjects will be questioned and evaluated for AEs or complications associated with the procedure. Complications of the injection include, but are not necessarily limited to: pain, swelling, erythema, bleeding and/or infection at the injection site. The Investigatory will determine the severity and relationship of each event, as defined above.

AEs observed during the course of this study, regardless of severity or relationship to the injection will be recorded on the CRF. Each reported complication/AE will also include the duration, action taken to address the AE, and the resolution status (e.g. ongoing, resolved). These subjects will continue to be evaluated for safety at all scheduled follow-up points.

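### Section 7.4 ties post-injection AE recording to unexpected symptoms while 8.1.1 requires all AEs, so known local reactions may be under-recorded and recorded unevenly

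*Protocol*

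**What the plan says.** Two parts of the protocol govern what is written down after the injection.

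- **Section 7.4, Post-Treatment Assessments and Instructions.** It opens without any filter: "Prior to leaving the clinic, the subject should be evaluated for local and non-local AEs". It then says "All post-treatment signs and symptoms that are unexpected should be recorded as AEs". The subject is briefed in the same terms: "The expected appearance of the index joint should be discussed with the subject with a request that all unexpected symptoms be reported" to the study team. Neither expected nor unexpected is defined.
- **Section 8.1.1, Adverse Events.** "All AEs that occur during or after injection will be recorded". The section requires all subjects to be questioned, applies at every assessment, disregards severity and relationship when deciding what goes on the CRF, and names pain, swelling, erythema, bleeding and infection at the injection site as complications.

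The safety endpoint (6.4) covers all AEs from injection to the 6-month assessment, and the design statement (6.5) gives the study's purpose as "to evaluate the residual risk of injections of MONOVISC for relief of pain". Section 4.2 lists "temporary injection site pain, swelling or tenderness" and temporary stiffness among the risks of any shoulder injection. It also says that the knee-trial events are expected to recur in the shoulder. Section 5.3 adds transient pain or swelling. SAP 4.4 tabulates AEs by severity, by relationship, and by local versus non-local site.

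**The concern.** The reactions most naturally called expected after an intra-articular injection are the ones that section 4.2 already lists. Applied literally, the 7.4 sentence gives a site grounds not to record them, and the briefing gives the subject grounds not to mention them. Section 8.1.1 points the other way, and the protocol does not say which section prevails.

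The AE incidence is the safety endpoint of a study whose stated purpose is residual risk. If sites read the two sections differently, the local AE count reflects reading habits as well as what happened to patients. The loss would fall mainly on mild, short-lived local reactions, which are plausibly the events most likely to be judged related. It would therefore reach the related-event summaries and the local versus non-local table in SAP 4.4. There is no control arm against which to notice a shortfall.

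**Working it through.** This is mainly a comparison of texts. The plan states no AE rate or expected AE count, so it has no figure of its own to reproduce.

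**Step 1. Which reactions could be treated as expected?** From 4.2: temporary injection-site pain, swelling or tenderness, and temporary shoulder stiffness. From 5.3: transient pain or swelling. Erythema is not in this group. Redness appears in 4.2 only as a symptom of a rare allergic reaction to contrast agent or local anesthetic.

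**Step 2. What does each section lead a site to do with such a reaction?**

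| Reaction | Known effect (4.2 or 5.3)? | 7.4 read literally | 8.1.1 |
|---|---|---|---|
| Injection-site pain | yes | may be left out | recorded, named |
| Injection-site swelling | yes | may be left out | recorded, named |
| Tenderness, stiffness | yes | may be left out | recorded, not named |
| Erythema | no | recorded | recorded, named |

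The sections disagree on the first three rows. The protocol text available gives no definition of an AE that would settle it.

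**Step 3. What later routes could recover a missed reaction?**

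- Questioning at follow-up (7.5, 8.1.1). The first visit after Day 0 is Month 1, so a reaction lasting days depends on recall. SAP table shells (4.1.2.1 and 4.1.3.4) show a 1 Week column, but the protocol schedule has no such visit.
- Diary (7.3.9.6): "Subjects will receive diary for to record rescue medications and concomitant medications". Symptoms are not included.
- New medications (7.3.9.3). The indication becomes an AE unless the condition is pre-existing. However, 7.4 foresees cold therapy or paracetamol for injection-site pain. Cold therapy is not a medication, and paracetamol is already the rescue drug (7.3.9.2), so its use may be logged as rescue.

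Each route is real but partial.

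**Step 4. How much could one site's reading matter?** With 25 subjects and up to 20 sites, the average at full spread is 25 / 20 = 1.25 subjects per site. Section 9.1 caps a site at 50% of enrollment, 0.5 × 25 = 12.5, so one site may hold 12 subjects. A single site's reading can decide almost half the safety denominator, while small sites contribute too few subjects to show a recording difference.

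**Step 5. Illustration on assumed rates.** Let p be the true proportion of subjects with a known local reaction and c the fraction recorded. Neither is in the documents. Expected number recorded = 25 × p × c. Probability that none is recorded = (1 − p × c)^25.

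| Assumed p | Full recording (c = 1) | Half recording (c = 0.5) | Chance of none recorded at c = 0.5 |
|---|---|---|---|
| 10% | 2.5 | 1.25 | 0.95^25 = 27.7% |
| 20% | 5 | 2.5 | 0.90^25 = 7.2% |
| 30% | 7.5 | 3.75 | 0.85^25 = 1.7% |

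Exact 95% intervals: 5 of 25 gives 6.8% to 40.7%; 2 of 25 gives 1.0% to 26.0%. The extreme case, 0 of 25, gives 0 to 1 − 0.025^(1/25) = 13.7%, which would exclude an assumed true rate of 20%.

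**The case against.** The strongest reply is that the plan already requires full capture. Section 8.1.1 is the dedicated AE section, it is unqualified, and it names local pain and swelling. The safety endpoint says all AEs, and AE assessment is scheduled at Baseline and at Months 1, 3 and 6. Section 7.4 itself begins with an evaluation for local and non-local AEs before the subject leaves. It never says that expected reactions are not to be recorded, and its briefing speaks of the joint's expected appearance, which may be narrower than the list in 4.2.

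Most of this stands, and it limits the point. A reader might infer that the plan restricts recording to unexpected events only, that a site with a swollen, painful shoulder in front of it records nothing, or that the plan removes the commonest events at capture. The documents do not support those readings. The word *only* does not appear in the instruction, the Day 0 evaluation covers local AEs, and 8.1.1 applies throughout. Nor do they support saying that incidence is biased downward as a fact. A count of 0 of 25 would need every site to disregard 8.1.1 and every later question to fail.

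The reply does not remove the conflict. The 7.4 sentence is the instruction staff use immediately after the injection, when these reactions begin. It gives a criterion that 8.1.1 lacks, and the subject's briefing carries the same criterion home for a month.

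**Conclusion.** The point holds as an internal contradiction. Section 7.4 and section 8.1.1 give different recording rules for known local reactions, the deciding term is undefined, and neither section is said to govern. The consequence is possible under-recording of short-lived local reactions and uneven recording across up to 20 sites. It bears on AE incidence and the SAP 4.4 tables; the primary efficacy analysis is not affected.

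The size cannot be derived from the documents. The figures in the working rest on assumed reaction rates of 10% to 30% and an assumed recording fraction, and show only that at 25 subjects a modest loss changes the picture visibly. The conclusion also rests on reading the reactions listed in 4.2 and 5.3 as those a site would call expected. That is a natural reading, but the protocol does not state it.

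**What to change.** Reconcile the two sections so that one rule applies. In 7.4, replace the recording sentence with wording such as: *All post-treatment signs and symptoms, whether expected or unexpected, are recorded as AEs in accordance with section 8.1.1.* Change the subject briefing so that subjects are asked to report all symptoms. The expected appearance of the joint can still be explained. The SAP 4.4 local versus non-local table should then draw on that single rule.

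The cost is a protocol wording change and a note to sites, with no extra visit. The downside is a higher reported count of mild local AEs.

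Optionally, a short symptom line could be added to the existing diary for the first days after injection and reviewed at Month 1. It would reduce dependence on recall, but it is new data collection with its own handling cost, and the contradiction can be resolved without it.

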7.5 Follow-Up Visits

All study subjects will have follow-up visits at 1, 3 and 6 Months after Baseline to evaluate the joint pain score and to assess adverse events.

The subject should be contacted at least 48 hours prior to their scheduled assessments to be reminded of the required assessment (and applicable wash out period) and to schedule the date and time of contact. At least three documented attempts will be made to contact the subject in order to accomplish maximum subject compliance with the follow-up schedule.

The following tests will be performed at the follow-up visits at 1, 3, and 6 months.

7.6 Follow-up Visits (± 7 days)

- Assess Concomitant Medications
- Assess Non- drug therapies
- Assessment of Adverse Events
- Assess Rescue Medication usage
- Confirm Rescue Medication Washout
 - If subject did not complete medications washout, reschedule the visit to allow washout to be completed.
- Collect and assess subject diary
- Patient Global Assessment (PGA)
- DASH index shoulder
- Index & Contralateral Shoulder Joint Pain (NRS)
- Physical Exam of Index and Contralateral Shoulder Joints

8. ADVERSE EVENTS

8.1 Reporting

8.1.1 Adverse Events

All AEs that occur during or after injection will be recorded. Worsening of a condition that existed prior to the study injection should be recorded as an AE. At each assessment during the trial, AEs that have occurred since the previous assessment must be recorded. All subjects will be questioned and evaluated for AEs or complications associated with the procedure. Complications of the injection include, but are not necessarily limited to: pain, swelling, erythema, bleeding and/or infection at the injection site. The Investigatory will determine the severity and relationship of each event, as defined above.

AEs observed during the course of this study, regardless of severity or relationship to the injection will be recorded on the CRF. Each reported complication/AE will also include the duration, action taken to address the AE, and the resolution status (e.g. ongoing, resolved). These subjects will continue to be evaluated for safety at all scheduled follow-up points.

8.1.2 Serious Adverse Events/Serious Adverse Device Effects

All SADE/SAEs must be reported to the Sponsor or designee within 24 hours of the investigative site becoming aware of its occurrence. This requirement is irrespective of whether the SADE/SAE is thought to be possibly related to the device or not.

9. STATISTICAL CONSIDERATIONS

9.1 Sample Size

The primary analysis will be the mean change in index joint pain from baseline to 6 months as measured by the Numerical Rating Scale.

The hypothesis to be tested is:

 H_0 : $\mu_{DMON} = 0$ versus H_A : $\mu_{DMON} > 0$.

In this hypothesis, μ_{DMON} is the mean change in pain from baseline at 6 Months in MONOVISC treated patients.

The data will be analyzed via a one sample t-test.

It is assumed that a mean change in pain from baseline of 2 points represents a clinically significant improvement with a standard deviation of 2 - 2.5 points, for 80% power and alpha of 5% then a total of 15 subjects are required. To ensure sufficient subjects are available at the 6 month follow up, it is proposed to enroll and treat at least 25 subjects which should be more than adequate to demonstrate that treatment of the study population with MONOVISC would reduce joint pain at 6 months.

Sites should not enroll more than 50% of the total enrollment.

9.2 Statistical Methods

Anika Therapeutics, Inc.

Tabulation of summary statistics, graphical presentations, and statistical analyses will be performed. Where not otherwise specified, the last pre-treatment observation will be used as baseline for calculating post-treatment changes from baseline. The primary presentations and analyses will be based on data pooled across index lesion locations and across study centers. Relevant summaries for individual lesion locations and centers, or combinations of index lesions and centers, may be presented for primary data. All testing and confidence intervals will use a significance level of 5%.

9.2.1 Demographic and Baseline Characteristics

All demographic and baseline characteristics will be tabulated by treatment group. Medical history findings, physical examinations and concomitant medications will be tabulated.

9.2.2 Adverse Events

Subjects with AEs will be summarized with frequencies and percentages by system organ class and preferred term, severity, and relationship to investigational product/procedure. In summaries of AEs by severity and relationship to investigational product/procedure, subjects reporting multiple episodes will be counted once under the worst severity and the strongest relationship, respectively. Serious Adverse Events will also be presented by relationship to investigational product/procedure.

Adverse events occurring prior to the index treatment will not be recorded in this trial.

9.2.3 Subject Populations

The Safety Population will be defined as all subjects who undergo Study Treatment, and the safety analysis will be performed on this population.

The primary analysis on the primary endpoint will be performed on the Intent to Treat (ITT) population, defined as all patients who were treated in the study. All Primary and Secondary endpoints will be analyzed using the ITT population.

A secondary analysis will be conducted on the Per Protocol (PP) population. Since the primary

endpoint is at 6 Months, this is all subjects who complete the 6 Month assessment and who do not have a major deviation from the protocol. For all other assessments, this is defined as the subjects who complete those assessments according to the protocol.

10. DATA MANAGEMENT CONSIDERATIONS

10.1Data Collection

The CRFs will be completed based on source documents. Once CRFs have been completed by the site, the data management group will begin the data cleaning process.

10.2Data Management

Once the CRFs are ready for review, the data management group will complete manual validation checks to ensure the quality, consistency, and completeness of all data entered. Instances of incomplete, uninterpretable or inconsistent data will be resolved with the site through issuing a query or other means of communication as necessary. The site is responsible to respond and / or correct the data for all queries issued in a timely manner. All queries and changes to the data will be tracked.

10.3Data Retention

All correspondence related to this clinical study should be archived in appropriate study files. Patient records including consent forms, source documents, CRFs, device records including regulatory authority (CA and IRB/EC) and Sponsor correspondence pertaining to the study must be kept on file. All original subject and device inventory records relating to the study shall be retained for not less than two years following notification by Anika Therapeutics, Inc. that the applicable regulatory authority approved an application for the marketing of the study device or that all investigations using the study device have been discontinued. Thereafter, records will not be destroyed without giving Anika Therapeutics, Inc. prior written notice.

11. CLINICAL SUPPLIES

11.1Packaging and Labeling

As MONOVISC is a released product and this is a PMCF, there are no requirements to maintain clinical trial material / device accountability.

The contents of the syringe are sterile if the syringe is intact. Each MONOVISC syringe is provided packaged in a sealed container within a carton and should not be used if the container has been opened or damaged.

The syringe, container and carton will have the required labeling information and caution statements.

The investigational sites are responsible for providing the paracetamol rescue medication to subjects.

11.2.Storage Requirements

The MONOVISC syringe should be stored as detailed in the Instructions for Use.

11.3 Instructions for Use

Version 2.0 14 Aug 2019 Confidential Page 22 of 38

Instructions for Use (IFU) are supplied with each MONOVISC syringe.

12. DATA QUALITY ASSURANCE

Anika Therapeutics, Inc. performs quality assurance checks on all clinical trials that it Sponsors. Before enrollment of a subject in this study, a monitor (from Anika or designee) and the site staff will review the protocol, the CRFs and instructions for completing them, the procedure for obtaining informed consent, the procedure for reporting AEs and all other relevant study procedures and forms.

